 SpO₂ and HR values corresponding to the same time points selected for the reference device will
 be chosen.

Clinical Investigational Plan		
Protocol No.:	Version 1.0	Page 16 of 45
01M2020-CH.LMD	Date: 22 December 2020	1 486 10 01 13

As a result, it is expected that from each enrolled subject up to 32 paired measurements of SpO_2 and HR will be obtained from the reference device and BrOxy M. Table 1 below summarises the data collection process.

Plateau no.	Range SpO₂ (%)	Inhaled solution	Plateau duration	No. of Measurements of SpO ₂ and HR extracted from recordings
1)	95 – 100 (target 97%)	Ambient air (medical air)	2.5'	8
II)	90 – 94 (target 92%)	O2 15% + N 85%	2.5'	8
III)	85 – 89 (target 87%)	O2 13% + N 87%	2.5'	8
IV)	80 – 84 (target 82%)	O2 11% +N 89%	2.5'	8
			Total	32 measurements

Table 1: Number of measurements to be performed for each subject, for each target level of SpO₂ and indication of the gaseous solution inhaled during each target level.

After completing the study on 10 subjects, collecting around 320 paired measurements it will be verified that, by dividing the desaturation interval into three equal parts, each part contains around a third of the measurements made. Therefore, considering the minimum target number of 200 measurements (per EN 80601-2-61 standard) and the interval between 98% and 82% of SaO_2 to be divided into three parts, at the end of the protocol on all the subjects recruited, it is expected to have:

- At least 67 measurements between 98% and 93% of SpO₂;
- At least 67 measurements between 92% and 87% of SpO₂;
- At least 67 measurements between 86% and 82% of SpO₂

In the event that this minimum target is not reached to meet the requirements of the EN 80601-2-61 standard, it may be necessary to recruit up to 2 additional subjects.

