10 STUDY SUBJECTS

The study population will include adult healthy volunteers who will accept to participate in this oxygen desaturation study in a controlled clinical environment. At least 11 healthy subjects will be enrolled. Data collected on the first subject will not be used for accuracy measurements but will serve to finalize the test set up phase and ensure adequate recording procedures are used by site staff. On each of the remaining 10 subjects, 32 paired measurements will be performed in order to obtain a maximum of 320 "valid" measurements (see Section 17.2) which guarantees a statistically significant accuracy study (see point EE2.3.4 of the ISO 80601-2-61: 2017 standard).

To take into account invalid data and potential drop out samples up to 2 additional subjects may need to be enrolled. For this reason sample size for this study will be between a minimum of 11 and a maximum of 13 healthy volunteers.

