16 STATISTICAL ANALYSIS

16.1 OVERVIEW

Statistical analyses will be performed with SPSS, Statistical Package for the Social Sciences (SPSS Inc, Chicago, IL), by following the requirements of the standard ISO 80601-2-61:2017 ("Medical electrical equipment - Part 2-61: particular requirements for basic safety and essential performance of pulse oximeter equipment, Procedure for non-invasive laboratory testing on healthy adult volunteers).

The *significance level*, that is the probability of rejecting the null hypothesis when it is true, will be set to 0.05 (two-sided, corresponding 5% risk of concluding that a difference exists when there is no actual difference).

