16.2 ANALYSIS SETS

Analyses will regard 320 pair measurements (80 in the ambient air, and 80 for each of the four defined target levels, that will be obtained from 10 healthy subjects).

Clinical Investigational Plan			
Protocol No.:	Version 1.0	Dana 25 of 45	
01M2020-CH.LMD	Date: 22 December 2020	Page 35 of 45	

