- Bland -Altman (B&A) plot, to evaluate the agreement between experimental and standard values; the B&A plot analysis is a simple way to evaluate a bias between the mean differences, and to estimate an agreement interval, within which 95% of the differences of the second method, compared to the first one, fall. Data can be analyzed both as unit differences plot and as percentage differences. The Bland-Altman chart is a scatterplot with the difference of the two measurements for each sample on the vertical axis and the average of the two measurements on the horizontal axis. Three horizontal reference lines are superimposed on the scatterplot one line at the average difference between the measurements, along with lines to mark the upper and lower control limits of plus and minus 1.96*the standard deviation of the measurement differences. Bland and Altman also discuss the option of using confidence interval bounds, based on the standard error of the mean, for the upper and lower reference lines. If the two methods are comparable, then differences should be small, with the mean of the differences close to 0, and show no systematic variation with the mean of the two measurements. 'Small' would be an amount that would be clinically insignificant for the factor being measured.

Clinical Investigational Plan			
Protocol No.:	Version 1.0	Page 36 of 45	
01M2020-CH.LMD	Date: 22 December 2020		

• Linear regression analysis: to give further information about any potential proportional bias about the mean differences and averages. It is a simple test for a linear trend, with the mean difference as dependent variable and the average difference as independent. The aim is to evaluate if the mean difference can be predicted from the average. The resulting coefficients indicate whether one can accept the null hypothesis that there is no proportional bias.

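### The Bland-Altman limits are rightly SD-based, but the plan leaves a standard-error alternative open for the same lines and makes no allowance for 32 readings per subject

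*Combined protocol and SAP*

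**What the plan says.** The Bland-Altman item in Section 16.3.2 gives the purpose of the interval: "to estimate an agreement interval, within which 95% of the differences of the second method, compared to the first one, fall". It then states how the plot is drawn, with a central line at the mean difference and "lines to mark the upper and lower control limits of plus and minus 1.96*the standard deviation of the measurement differences". The following sentence notes that the method's authors raise an alternative: "using confidence interval bounds, based on the standard error of the mean, for the upper and lower reference lines". The plan does not say that it will use this option. Nor does it rule it out, or confine it to a confidence interval for the mean difference.

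On the data, Section 16.2 says "Analyses will regard 320 pair measurements". Section 10 explains where they come from: "On each of the remaining 10 subjects, 32 paired measurements will be performed in order to obtain a maximum of 320". Section 3 and the Synopsis give 200 measurements as the minimum target. Section 16 describes no method that allows for repeated readings on the same subject.

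**The concern.** Two different quantities are named for the same pair of lines. An interval of ±1.96 SD describes the spread of individual differences, which is what a user of a single reading needs. An interval built from the standard error of the mean describes the uncertainty of the average bias, and it shrinks as readings accumulate. It cannot meet the plan's own definition of an interval holding 95% of the differences.

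Section 16 gives no numerical acceptance limit for accuracy. Small differences are described only as clinically unimportant ones, without a figure, so readers will judge individual-reading error largely from this band. Lines based on the standard error would make the device look far more precise than it is.

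The second matter is separate. Any standard error for the bias, whether in a confidence interval or in the paired t test of the same section, depends on how many independent units there are. The plan speaks of 320 pairs, but there are 10 subjects.

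**Working it through.** **Inputs**
- Rule for the lines: mean difference ±1.96 SD (Section 16.3.2).
- Pairs: 4 plateaus × 8 = 32 per subject (Table 1), 10 subjects (Section 10), 320 in all (Section 16.2). Section 10 calls 320 a maximum.
- Minimum number of pairs: 200 (Section 3).
- SD of the differences: not given. It cancels in every ratio below.
- Intraclass correlation (ICC) of the differences within a subject: not given. Assumed, with a range shown.

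**Step 1: the plan's own figures.** For normal differences, 2Φ(1.96) − 1 = 0.950, so ±1.96 SD gives the stated 95%. 10 × 32 = 320. Both reproduce.

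**Step 2: lines from a naive standard error.** The half-width is 1.96 × SD/√n, so the SD limits are wider by √n. The coverage of individual differences is 2Φ(1.96/√n) − 1.
- n = 320: √320 = 17.9, half-width 0.110 SD, coverage 8.7%.
- n = 200: √200 = 14.1, half-width 0.139 SD, coverage 11.0%.
- n = 80 (one plateau): √80 = 8.9, half-width 0.219 SD, coverage about 17%.

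**Step 3: allowing for 32 readings per subject.** With equal correlation among a subject's readings, the design effect is 1 + 31 × ICC and the effective sample size is 320/(1 + 31 × ICC). The naive standard error is too small by √(1 + 31 × ICC). Lines from the adjusted standard error are narrower than the SD limits by the square root of the effective sample size.

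| Assumed ICC | Design effect | Effective n | Naive SE too small by | Adjusted-SE lines narrower than SD limits by | Coverage |
|---|---|---|---|---|---|
| 0.1 | 4.1 | 78.0 | 2.0 | 8.8 | 17.6% |
| 0.3 | 10.3 | 31.1 | 3.2 | 5.6 | 27.5% |
| 0.5 | 16.5 | 19.4 | 4.1 | 4.4 | 34.4% |
| 1.0 | 32.0 | 10.0 | 5.7 | 3.2 | 46.5% |

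The last two columns use the normal quantile. With the t quantile on 9 degrees of freedom, the narrowing at ICC 0.1 to 1.0 becomes about 7.7 to 2.7 times.

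**Step 4: effect of pooling on the SD limits.** If σ² is the total variance, the expected pooled variance is σ² × (320/319) × [1 − (1 + 31 × ICC)/320] = σ² × (319 − 31 × ICC)/319 = σ² × (1 − 0.097 × ICC). Even at ICC = 1 the SD is multiplied by √0.903 = 0.950, which is an understatement of about 5%. At ICC 0.3 the factor is √0.971 = 0.985, about 1.5%.

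**The case against.** The strongest reply is that the plan already does the right thing. It states the ±1.96 SD rule as the way the plot is drawn. The standard-error sentence reports what the method's authors discuss and lacks the permissive wording found elsewhere in Section 16.3, for example where the plan says that data can be analysed as unit or as percentage differences. A reader might infer that the plan allows standard-error lines as limits of agreement, or lets the sponsor choose after seeing the data. The text does not support that: one rule is stated, and replacing it would depart from it. This part of the objection stands, and it reduces the first matter to one of clear wording.

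The sentence might also be a loose reference to confidence intervals around the limits, which would be good practice. The mention of the standard error of the mean counts against this reading, but the ambiguity is itself a reason to rewrite the sentence.

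Third, no pass/fail criterion is tied to these lines, the item is one of five unranked routines, and a plot with about 91% of its points outside the lines would show the misuse. That stands too, and it limits the harm.

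Fourth, the factor of 18 belongs to one scenario: 320 pairs and a naive standard error. This is also right, so the range is given above. Every scenario leaves the lines too narrow to serve as limits of agreement.

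None of this answers the separate point that Section 16 makes no provision for repeated readings within subjects.

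**Conclusion.** This is a cheap improvement, not a failure of the specified method. The SD-based limits are correctly defined. The defect is a sentence that leaves an unsuitable alternative open for the same two lines. If it were used, the lines would be about 18 times too narrow at 320 pairs, about 14 times at 200, and about 3 to 9 times even with a standard error adjusted for subjects.

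The more substantive gap is that nothing allows for 32 readings on each of 10 subjects. A standard error or confidence interval for the bias that treats 320 readings as independent is too small by about 2.0 times at ICC 0.1, 3.2 at 0.3 and 4.1 at 0.5. A reader might infer that clustering also invalidates the limits of agreement. It does not: pooling understates their SD by at most about 5%.

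These sizes assume normal differences, 32 valid pairs on each of 10 subjects and equal correlation among a subject's readings. The ICC values are assumptions, because the documents give none.

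**What to change.** In Section 16.3.2:
- Delete the standard-error option as a definition of the upper and lower lines.
- Keep the limits of agreement at bias ±1.96 × total SD, where the total SD is the square root of the sum of the between-subject and within-subject variances from a model with a random effect for subject.
- Report 95% confidence intervals for the bias and for each limit separately, labelled as such and based on the number of subjects (10, or however many are analysed) rather than the number of readings.

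The cost is one rewritten sentence and a standard repeated-measures model. The downside is a little more analysis work and wider, less favourable confidence intervals. No extra subjects, visits or measurements are needed.

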The following routines will be used: the paired t test, to evaluate the differences between experimental and standard values; correlation analysis, to quantify the degree to which experimental and standard values are related; concordance correlation coefficient (CCC), to evaluate whether the experimental value is interchangeable with the standard; Bland -Altman (B&A) plot, to evaluate the agreement between experimental and standard values; linear regression analysis to give further information about any potential proportional bias about the mean differences and averages.

^{*} ECG required at screening unless a 12-lead ECG has been performed in the last 2 months prior to screening

^{**}pregnancy test only for pre-menopausal women.

Protocol No.: Version 1.0

01M2020-CH.LMD Date: 22 December 2020

Page 13 of 45

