6 REFERENCE MEDICAL DEVICE

The device used as the reference for measuring SpO₂ and heart rate is the Nellcor™ Bedside Respiratory Patient Monitoring System model PM1000N (Covidien LLC, USA). It is a CE marked device normally used in a hospital environment for monitoring patients while they are in bed. The Nellcor pulseoxymeter will require the use of the Nellcor™ Adult XL SpO₂ Sensor mod. MAXALI (sterile, single-use only).

In addition to being a precise device for measuring HR and SpO₂, it allows the storage of the displayed measurements and the downloading of data on a PC memory via USB. These features make the Nellcor™ mod. PM1000N suitable to be employed as reference device in this clinical trial.

The main features of the Nellcor mod. PM1000N are as follows:

- Precision on adult subjects, even with low perfusion:
 - Error +/- 2 digits, on the 70-100% range of SpO₂;
 - Error +/- 3 bpm, on the 20-250 bpm range of HR;
 - The measurements used as a reference were carried out on healthy, voluntary subjects, by means of the use of a CO-oximeter with analysis of arterial blood samples.
- Data and measurement recording:
 - Up to 48 hours of recording
 - Sampling: 1 measure per second
 - USB connection to download recorded data (SpO₂ and heart rate recorded values) by means of specific software;
 - Downloaded data shows time indication (hour, minute and second) and operating status, indicating signal quality such as motion, alarms, loss of pulse, etc.
- Alarms:
 - Acoustic and visual feedback to report critical conditions;
 - Possibility to customize the alarm levels (for threshold value and minimum duration of the event);
- Product compliance:
 - o IEC 60601-1:2005

Clinical Investigational Plan			
Protocol No.:	Version 1.0	Page 21 of 45	
01M2020-CH.LMD	Date: 22 December 2020	1 agc 21 01 43	

o IEC 60601-1-2: 2007

o IEC 80601-2-61:2001

The rationale for the selection of the reference device is that it meets the requirements specified in the standard ISO 80601-2-61:2017, section EE.3. In particular, the Nellcor™ Bedside Respiratory Patient Monitoring System model PM1000N has been calibrated against:

1) a Co-Oximeter for measuring \mbox{SpO}_2 and

2) an ECG for measuring cardiac frequency.

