11.2 VISIT 1 – TEST SESSION (DAY 1)

The study involves, starting from medical air (O2 concentration 20.98%), the subsequent use of cylinders with an oxygen concentration of 15%, 13% and 11%, rest nitrogen. We will use a Hans Rudolph one-way valve connected to the subject with a nose piece to eliminate nasal ventilation and with a disposable mouthpiece and filter. The valve on the inhalation side will be connected, with a two-way tap, to a Douglas bag supplied by the gas cylinder with a concentration selected according to the target level of SpO_2 to be obtained (see Table 1).

From each session of measurements on each subject, the photoplethysmographic signals in the red and infrared frequency will be collected from the subject's wrist, while the comparison measurements will be carried out using the reference oximeter.

As shown in Figure 1, during the execution of the protocol, four different saturation plateaus will be used (in steps of 5% and, therefore, at 97%, 92%, 87% and 82%), waiting 30" before starting to keep the SpO₂ level on each plateau for 2.5' in order to obtain 8 measurements in post-processing. These measurements will be at least 20" away from each other, for a total of 32 measurements for each subject as summarized in Table 1 (on page 17 and replicated below).

Plateau no.	Range SpO₂ (%)	Inhaled solution	Plateau duration	N. of Measurements of SpO ₂ and HR extracted from recordings
1)	95 – 100 (target 97%)	Ambient air (medical air)	2.5'	8
II)	90 – 94 (target 92%)	O2 15% + N 85%	2.5'	8
III)	85 – 89 (target 87%)	O2 13% + N 87%	2.5'	8
IV)	80 – 84 (target 82%)	O2 11% +N 89%	2.5'	8
			Total	32 measurements

Clinical Investigational Plan			
Protocol No.:	Version 1.0	Page 28 of 45	
01M2020-CH.LMD	Date: 22 December 2020	rage 28 01 43	

Table 1: Number of measurements to be performed for each subject, for each target level of SpO₂ and indication of the gaseous solution inhaled during each target level.

[figure not shown]

Figure 1: Time distribution of the SpO_2 measurements to be carried out on each individual subject. Four different saturation plateaus will be used, waiting the plateau stabilization before starting the 2.5' signal recording from which the series of 8 measurements with at least 20' of pause are extracted by means of a post-processing algorithm.

Before starting the measurement protocol, as shown in Figure 1, in order to prepare the above instrumentation, it is necessary to carry out the following operations:

- 1. Start the PC;

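### The proportional-bias regression lets a non-significant slope stand as absence of bias, on a predictor that is misnamed and detects SpO₂ under-tracking poorly

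*Combined protocol and SAP*

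**What the plan says.** Section 16.3.2 lists five routines for the primary endpoint: paired t test, correlation, concordance correlation coefficient (CCC), Bland-Altman plot and a linear regression. The regression is specified "with the mean difference as dependent variable and the average difference as independent". The sentence after it, and the Bland-Altman description before it, show that the intended predictor is the average of the BrOxy M and reference readings. The decision rule is "The resulting coefficients indicate whether one can accept the null hypothesis that there is no proportional bias". The synopsis describes the same routine as "linear regression analysis to give further information about any potential proportional bias about the mean differences and averages". Section 16.1 sets a two-sided significance level of 0.05.

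No margin for the slope, no confidence-interval criterion and no estimate of BrOxy M noise is given. The Bland-Altman text asks for small differences but puts no number on small.

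Section 17.2 accepts SpO₂ values only from 80 to 100%. The plateau targets in Section 11.2 are "in steps of 5% and, therefore, at 97%, 92%, 87% and 82" percent, so the lowest lies 2 points above the lower limit and the highest 3 points below the upper one.

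**The concern.** There are three difficulties.

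- **Wording.** Read literally, the predictor is itself a difference, and the trend test cannot be run that way.
- **Inference.** Failing to reject is not evidence of no proportional bias. With no margin and no interval, a noisy comparison is the easiest way to reach the favourable statement.
- **Predictor.** The covariance between the difference and the average of two readings is half the difference of their variances. Unequal random error therefore moves the slope even when there is no proportional bias. Nothing in the documents makes the errors equal: BrOxy M is a reflection sensor on the wrist, and the reference is a bedside monitor read at the index finger. If BrOxy M is the noisier device, the shift is upward, against the negative slope that marks under-tracking (BrOxy M falling less than true saturation).

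At stake is whether the report can say that BrOxy M follows saturation down. The t test can miss errors of opposite sign at high and low saturation, and CCC and limits of agreement do not isolate a slope.

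**Working it through.** **Inputs from the documents.** Section 16.2: "Analyses will regard 320 pair measurements". Section 11.2: four plateaus, each held "in order to obtain 8 measurements in post-processing". Reproducing the count: 10 subjects × 4 plateaus × 8 = 320, with ambient air as plateau I. The targets 97, 92, 87 and 82 have mean 89.5, variance (7.5² + 2.5² + 2.5² + 7.5²)/4 = 31.25 and span 15 points. The reference specification in Section 6 is "Error +/- 2 digits, on the 70-100% range of" SpO₂; whether that is one SD or a bound is not stated.

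**Assumptions.** Reference error SD 1; BrOxy M error SD 1.5 to 3; wander of the true level within a plateau SD 0.7; independent pairs; errors independent of the true level.

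**Slope on the average, no range filter.** Write V = 31.25 + 0.7² = 31.74, sr and sb for the reference and BrOxy M error SDs, and b = 1 + true slope. The expected slope is

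{[(b² − 1)V + sb² − sr²]/2} ÷ {[(1 + b)²V + sb² + sr²]/4}.

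- No bias (b = 1), SDs 1 and 2: 1.5/(31.74 + 1.25) = 0.045.
- No bias, SDs 1 and 3: 4/(31.74 + 2.5) = 0.117.
- True slope −0.12 (b = 0.88), SDs 1 and 3: numerator (−0.2256 × 31.74 + 8)/2 = 0.42; denominator (3.5344 × 31.74 + 10)/4 = 30.5; slope about +0.01. The real bias has been cancelled.

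Simulation without the filter agrees: with no bias the test rejects in 19%, 53% and 98% of trials at BrOxy M SD 1.5, 2 and 3. With equal noise it holds its level.

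**With the 80–100% range on both readings.** Trimming removes low BrOxy M readings at the 82% plateau and high ones at the 97% plateau, which pulls the slope down and offsets the noise effect. With no bias, rejection falls to 2–4%. For real under-tracking:

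| True slope | BrOxy M SD | Bias over 15 points | Detected, no filter | Detected, filter on both |
|---|---|---|---|---|
| −0.05 | 2 | 0.75 | 4–6% | about 38% |
| −0.08 | 2.5 | 1.2 | 4–6% | about 51% |
| −0.12 | 3 | 1.8 | 4–6% | about 65% |

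The third column is slope × 15. With the filter, about 62%, 49% and 35% of trials would end in a statement of no proportional bias.

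**Nominal plateau level as predictor.**

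- Filter on both readings: the same trimming makes an unbiased BrOxy M look compressed. False slopes are −0.018, −0.045 and −0.120 at SD 1.5, 2 and 3, with false rejection of about 15%, 51% and 98–99%.
- Range applied to the reference reading only: false rejection returns to about 5–7%, and the −0.12 case is detected in about 94–95% of trials.

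**The case against.** The strongest reply is that plotting and regressing against the average is the ordinary Bland-Altman choice, and that under the protocol's own validity range the test does not raise false alarms. That stands. A reader might infer from the algebra that unequal noise will produce a spurious bias signal in most trials, or that real under-tracking will almost always be hidden. Both hold only if the 80–100% range is ignored. With it, false rejection is 2–4% and detection is 38–65%, not 4–6%. Varying the wander (SD 0.3 or 1.5) or raising the reference SD to 2 leaves false rejection at 1.5–3.6%.

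A reader might also infer that changing the predictor is enough. It is not: with BrOxy M readings still filtered, nominal level does worse under the null than the planned test.

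It is also fair that BrOxy M noise appears nowhere in the documents, that the regression is offered only as further information, that the plot is separately to be inspected for systematic variation with the mean, and that a scale shift lowers the CCC. These points limit the severity. They do not justify accepting the null from a non-significant coefficient, and they do not repair the literal predictor.

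**Conclusion.** The point holds at moderate weight. Two parts rest on the text alone: the predictor is misnamed, and non-significance is allowed to establish absence of proportional bias. The third, weak detection of under-tracking, depends on assumed noise. At reference SD 1 and BrOxy M SD 2 to 3, relative over-reading of 0.75 to 1.8 points across the desaturation is missed in roughly 35–62% of trials. Noise levels closer together would distort less. If BrOxy M were the quieter device, over-response would be masked instead of under-tracking.

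The simulations treat the 320 pairs as independent; clustering within 10 subjects would make the p-values less reliable still. The documents do not support calling the planned test prone to false signals, or calling this a must-fix: no pass/fail decision is attached to the coefficient.

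**What to change.** In Section 16.3.2, with the synopsis aligned:

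1. Delete the sentence that accepts the null from the coefficients. Report the SpO₂ slope with its 95% CI, expressed as points of bias per 15-point desaturation, and state that non-significance will not be read as absence of bias.
2. Correct the predictor wording. Regress BrOxy M minus reference on nominal plateau level (97, 92, 87, 82), with subject random intercept and random slope. With intercepts only, an assumed between-subject slope SD of 0.05–0.10 gave 11–23% false rejection (no range filter). Do not substitute the reference reading as predictor: its own error biases the slope (31% false rejection at reference SD 1 and BrOxy M SD 2, no filter).
3. For this regression, do not drop a pair because BrOxy M reads outside 80–100%; apply that range to the reference reading only. Item 2 should not be adopted without this.

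The predictor change is for SpO₂. No HR level is imposed, so it does not carry over to HR, but the wording change in item 1 does.

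The cost is one changed model and one extra analysis-data rule, with no new measurements. BrOxy M values outside the range must be kept in the extracted data. For shallow slopes the gain in detection is smaller, which is a further reason to rely on the interval.
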